## 8.10 Internal pilot

The trial will have an internal pilot phase that will test the recruitment of sites and participants against agreed milestones, and a formal review will take place 6 months after the first

randomisation. At the end of the internal pilot, we project to recruit a minimum of 74 participants. *Table 8* below denotes the progression criteria, along with actions that will be undertaken for each category.

*Table 8 progression criteria for pilot study*

Progression criteria	Red	Amber	Green
Recruitment rate/site/month	<1	1 - 2.3	≥2.4
Number of sites opened	<3	3 – 4	5 - 8
Total number of participants	<40	40 – 73	≥74
Action	Consider stopping the trial*	Improvement required	Continue, no action needed

*\*Utilise information from qualitative sub-study to identify barriers to recruitment; liaise with Trial Steering Committee and sites to strengthen recruitment strategy via relevant publicity and understanding any issues at local sites.*

## 9 DATA MANAGEMENT PLAN

Full details about data management will be provided in the *Data Management Plan (DMP)* which will be finalised prior to commencement of recruitment.

### 9.1 General

Data handling, validation specifications, source data verification, data storage and protection steps along with other data related procedures will be detailed in the trial DMP.

### 9.2 Data Capture and Data Queries

All trial data will be entered onto the electronic Case Report Forms (e-CRFs) in the trial specific database (REDCap, a secure web platform for building and managing online databases), developed and locally hosted by NCTU. Participants will be identified on the database with their unique trial number and initials.

The trial data collected at clinic visits will be entered directly on the database by site staff. Where access to the online database system is not available, paper worksheets can be used to collate data, which will then be transcribed onto the trial database. The site staff who have access to the trial database will have a designated data entry role on the trial Delegation and Responsibilities Log. Entry to the database will be password protected. PIs signature on e-CRFs will be collected via the database.

Fortnightly text messages/emails/app notifications will be sent to participants for a year to collect information about number of flares and time to first flare. Text messages will be sent to either parent/guardian or adolescent, depending on their preference. The data that will be used will be initial response received, i.e. if a child response to the questionnaire first that would be the data analysed and vice versa. Participants responding via text and email will be sent a link and those using the app will enter responses directly in response to notifications. Entered responses will be automatically uploaded onto the trial database, REDCap.

Normal route of collection of questionnaire data will be via app or web, where participants will enter their answers directly, but if preferred, the central management team at NCTU will post paper questionnaire booklets to the participant's address along with the FREEPOST envelope. Completed questionnaires will be received at NCTU where the answers will be transcribed onto the database.

The access to the database will be controlled with unique log-in usernames and passwords for each member of the research team. The staff will be trained on completion of e-CRFs and data entry on the electronic system. E-CRF completion guidelines will be provided to the sites. The CI will be given access to the trial database and will be able to sign off the expectedness and causality of SAEs electronically, where relevant. PIs at sites will ensure that the e-CRFs have been completed correctly and that the data is accurate. This will be evidenced by the signature of the site's Principal Investigator on the e-CRF.

### 9.3 Description of Data Entry Validation

The database used for the purposes of this trial will be Redcap®. Access to the database will be restricted and secure. The trial database will have built-in validation steps to alert or restrict non-sensical and ambiguous data entry. Any missing and ambiguous data will be queried with the site via e-CRFs. Sites should respond to the data queries in a timely manner, ideally within 2 weeks of the query being raised. All access and data transactions will be logged on the database via a full audit trail.

### 9.4 Data Cleaning and Database Lock

Participant's e-CRF data will be reviewed as soon as they are confirmed with validation rules, missing data have been obtained and all data passed through validation checks (i.e. there are no data queries outstanding). At the end of the trial, prior to the data analysis, the data will be validated, and the trial database will be locked to prevent amendment to the data collected. The rules of the data validation and soft/hard database locks are described in the *Data Management Plan* as part of the internal quality management process.

### 9.5 Monitoring

Details of trial monitoring will be described in detail in the trial *Monitoring Plan*.

Central monitoring will be carried out on a regular basis based on the trial *Monitoring Plan* and *Risk Assessment* following a risk assessment and as documented in the PEARLS Trial *Monitoring Plan*, whilst onsite monitoring may be triggered, for example by poor data return, poor data quality, lower/higher than expected SAE reporting rates, or excessive number of participant withdrawals or deviations. If an on-site monitoring visit is required, NCTU will contact the site to arrange a date for the proposed visit and will provide the site with written confirmation. NCTU will be in regular contact with each site's research team to check on progress and address any queries that they may have. Central monitoring will include regular checks for incoming e-CRF data for adherence with the protocol, data consistency, missing data and timing. Sites will be asked for missing data or clarification of inconsistencies or discrepancies.

Investigators will allow NCTU trial/monitoring staff access to source documents as requested. Sites will be requested to provide copies of signed ICFs and other documentation for in-house review for central monitoring for all participants.

## 10 STATISTICAL CONSIDERATIONS

### 10.1 Sample size and justification

Using data from a subset of 211 women with LS surveyed in preparation for the funding application for this trial who would be broadly eligible, the mean (SD) number of flares in this group was estimated to be 4.0 (2.8) per year. The data showed evidence of overdispersion (variance larger than the mean) hence a negative binomial regression would be appropriate for the data. Assuming an event rate of 4 flares per patient per year, a sample size of 320 would be required to detect a relative reduction of 25% in number of flares in the intervention group to 3 flares per patient per year (absolute reduction of 1 flare per patient in a year), with 90% power, 1:1 allocation and a two-sided significance level of 0.05, using dispersion parameter value of 0.34 estimated from the survey data. A relative reduction in number of symptom flares by 25% is considered meaningful by patients and clinicians since eligible patients have controlled LS so even a small reduction in number of flares would be meaningful to them. Loss to follow-up is expected to be around 5-10% [35-38]. Inflating the sample size by 20% to account for both non-collection of primary outcome data and treatment non-compliance, PEARLS aims to randomise 400 participants.

### 10.2 Analysis of outcome measures

The reporting of the trial will be in accordance with CONSORT guidelines. A full statistical analysis plan (SAP) will be developed and agreed with the Trial Steering Committee (TSC) prior to database lock.

Appropriate descriptive statistics for the demographic and clinical outcome measures at baseline will be used to assess balance between the randomised arms at baseline. Descriptive statistics appropriate for the outcome will also be presented for all outcomes at all collected time points by treatment arm.

Primary analysis will compare the average number of flares per person-time between the treatment groups, with analysis according to the allocated treatment strategy regardless of adherence to the strategy (intention-to-treat). Negative binomial regression, adjusted for minimisation factors and incorporating exposure time (person-time), will be used to calculate the incident rate ratio and 95% confidence interval. Supplementary analyses for the primary outcomes will use per-protocol or complier average causal effect (CACE) analysis if possible to estimate the effect of the intervention among the participants who would comply with their allocated intervention. Subgroup analyses for the primary outcome will be performed according to age at randomisation (children or adult), time since last flare, and strength of prescribed TCS (potent or superpotent), by including appropriate interaction terms in the primary model, however, results will be regarded as exploratory as the trial is not powered to detect interactions. Any additional sub-groups to be explored will be pre-specified in the SAP.

Between-group comparison of secondary outcomes will be based on an appropriate regression model for the outcome (or appropriate non-parametric estimator), adjusted for the same variables as the primary analysis.

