## 5 RANDOMISATION AND BLINDING

Upon entry to the trial, participants will be individually allocated in a 1:1 ratio to either proactive or reactive use of TCS. The strategies of treatment will be assigned randomly using a minimisation algorithm with a random element, balancing across groups on:

- Recruitment by site
- Age at randomisation (prepubertal – 5 to <12 years, adolescent - 12 to <16 years, adult - 16 to <45 years, perimenopausal 45 years & above)
- Time since last flare ( $\leq 6$  months,  $> 6$  months)
- Strength of study TCS (potent or superpotent)

The trial arm allocation will be concealed using a web-based algorithm and will be held on a secure server at the Nottingham Clinical Trial Unit (NCTU). The randomisation will be accessed via a secure website developed and maintained by NCTU. Unique usernames and passwords will be provided to those who are delegated the role of randomising participants using the web-based system. Randomisation can be performed by suitably trained site research staff assigned this task on the *Delegation of Responsibilities Log*, following confirmation of each individual participant's eligibility by a clinician.

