### Baseline

#### Visit 1

(at baseline)

- Informed consent
- Eligibility check and confirmation
- Contact details
- Collection of baseline data:
  - Concomitant medication (relevant to condition) and relevant medical history
  - Demographic information
  - Clinician global severity assessment
  - Scarring assessment (VASS, clinical examination)
  - Vulval development and scarring (in adolescents and children)
  - Condition specific QoL (VQLI or CDQLI)
  - Health related QoL assessed by EQ-5D-5L in adolescents/adults and CHU-9D in children
  - Bespoke resource use questionnaire and healthcare questionnaire
- Clinical photographs, or clinical diagram if consent for photographs not taken
- Randomisation

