## 8.7 Trial assessments\*

Table 7. Data collection timepoints

Trial assessment	Source	Timepoint and visit number					
		Screening/baseline Visit 1	3 month Visit 2	6 month Visit 3	12 month Visit 4	18 month Visit 5	24 month Visit 6
Confirmation of eligibility	Medical notes/clinician/participant	X					
Consent	Participant	X					
Randomisation	Participant	X					
Medical history	Participant/medical notes	X					
Demographic information	Participant/medical notes	X					
Concomitant medication (relevant to condition only)	Participant	X	X	X	X	X	X
Number of flares and time to 1st flare	Participant	Starting 2 weeks from randomisation, every 2 weeks for 12 months					
Progression of scarring via photograph (optional), VASS and examination	Clinician	X **			X €		X €
Vulval development and scarring (adolescents and children)	X	X	X	X	X	X	X
Clinical global severity assessment	Clinician	X	X	X	X μ	X	X μ
Condition specific Quality of Life (VQLI or CDLQI)	Participant	X	X	X	X	X	X
Health related quality of life (generic utility instrument) (EQ-5D-5L in adolescents/adults or CHU-9D in children)	Participant	X	X	X	X	X	X
Sexual function using Female Sexual Function Index (adults only)	Participant				X		X
Acceptability of treatment	Participant				X		X
Adherence to treatment	Participant		X	X	X	X	X
Resource use (bespoke and healthcare)	Participant	X	X	X	X	X	X
VIN or vulval SCC	Clinician						X
Adverse effects of therapy	Participant, Clinician		X	X	X	X	X
Change/cessation of therapy	Participant		X	X	X	X	X
* Definition of age groups for purpose of assessments is described in section 4.4		° At 12 and 24 months assessed by blinded assessor					
** Assessed by photographs (if consented) or clinical assessment diagram		μ At 12 and 24 months assessed by treating clinician and blinded assessor					
€ Clinical assessment comparing to baseline photographs (if consent given for photographs) or to baseline clinical assessment diagram if consent for photographs not obtained							

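### The stated covariate rule for secondary outcomes omits the baseline score of VASS, VQLI, CDLQI and clinician global severity, although each is measured at Visit 1

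*Protocol*

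**What the plan says.** **Covariates.** Section 10.2 specifies the primary model as "Negative binomial regression, adjusted for minimisation factors and incorporating exposure time (person-time)". Secondary outcomes get a regression model suited to the outcome, or a non-parametric estimator, "adjusted for the same variables as the primary analysis". The statistical methods entry in the synopsis gives the same rule.

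**What those variables are.** Section 5 lists four minimisation factors: "Recruitment by site", age band at randomisation (four levels), "Time since last flare" (up to or beyond 6 months), and potency of the study steroid (two levels).

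**What is measured at baseline.** The Visit 1 list in section 8.1 includes "Scarring assessment (VASS, clinical examination)", the clinician global severity assessment and the condition-specific quality-of-life score. Table 7 in section 8.7 agrees.

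**How baseline outcome values are used.** Section 10.2 gives them a descriptive role, to show balance between arms. Adjustment for baseline is mentioned only in section 12, for QALYs, where results are planned with and without it.

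**FSFI.** The Table 7 row "Sexual function using Female Sexual Function Index (adults only)" is marked at 12 and 24 months only, and FSFI is absent from the Visit 1 list.

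**The concern.** For a scale measured both before and after randomisation, the baseline score is usually the strongest single predictor of the follow-up score. A model that omits it carries more residual variance than necessary, and any chance difference between arms at entry passes into the estimated effect.

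VASS shows this most clearly. Section 1.1 describes scarring as not reversible except by surgery, so a participant's VASS at 12 or 24 months should largely carry forward the architecture present at entry. Minimisation does not balance on scarring. VASS serves secondary objective 1 (disease progression). Global severity and the quality-of-life scores serve objective 2.

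At stake are the width of the confidence intervals on these secondary outcomes and their exposure to chance imbalance.

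**Working it through.** **1. The plan's own figure.** No sample size or power is stated for any secondary outcome. The only figure is the primary one in section 10.1: 320 analysed, 400 randomised. With rates 4 and 3 per year, dispersion 0.34, two-sided 0.05 and 90% power:

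- null variance term at the pooled rate 3.5: 2/3.5 + 2 × 0.34 = 1.251
- alternative variance term: 1/4 + 1/3 + 2 × 0.34 = 1.263
- n per arm = (1.960 × √1.251 + 1.282 × √1.263)² / (ln 0.75)² = 159.5, so 160 per arm and 320 in total
- 320 / (1 − 0.20) = 400

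A version based on the likelihood-ratio divergence gives 322. The stated figure reproduces, and this point does not touch it.

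**2. Which outcomes are affected.**

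| Secondary outcome | Own value at Visit 1? | Covered by the stated covariates? |
|---|---|---|
| VASS | Yes | No |
| VQLI (adults), CDLQI (under 16) | Yes | No |
| Clinician global severity (5-point) | Yes | No |
| Yes/no scarring progression | Judged against baseline photograph or diagram | Baseline is built into the endpoint |
| Time to first flare, VIN/SCC | No baseline value exists | Not applicable |
| FSFI | Not collected | Cannot be adjusted |

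**3. Size for continuous scores.** Let ρ be the correlation between baseline and follow-up that remains after the minimisation factors, which are already in the model. The documents give no value, so 0.3 to 0.7 is an assumption. Adding the baseline score multiplies the residual variance by 1 − ρ² and the standard error by √(1 − ρ²).

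The difference detectable with 90% power at two-sided 0.05, in residual SD units and with N analysed, is (1.960 + 1.282) × √(4/N) × √(1 − ρ²). With N = 320 and no baseline term this is 3.242 × 0.1118 = 0.362 SD.

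| Assumed ρ | Variance multiplier | SE multiplier | Detectable difference, N = 320 | Unadjusted N of equal precision, 320/(1 − ρ²) | Power for an illustrative 0.3 SD |
|---|---|---|---|---|---|
| none | 1 | 1 | 0.362 SD | 320 | 0.77 |
| 0.3 | 0.91 | 0.95 | 0.346 SD | 352 | 0.80 |
| 0.5 | 0.75 | 0.87 | 0.314 SD | 427 | 0.87 |
| 0.7 | 0.51 | 0.71 | 0.259 SD | 627 | 0.96 |

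**4. Limits of the table.** N = 320 is the target for the primary analysis. VQLI is for adults and CDLQI for those under 16, so each has fewer participants and a larger detectable difference. The multipliers do not depend on N.

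The formula is for a linear model. It does not transfer directly to the 5-point global severity scale.

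**The case against.** **The sentence is generic and a SAP is still to come.** One line covers binary, ordinal, time-to-event and continuous outcomes. It does not say that no other covariate may enter, and section 10.2 promises a full SAP agreed with the TSC before database lock, which could add baseline scores. This tempers the point but does not remove it. The protocol leaves the type of model open but names the covariate set, so a SAP that added baseline scores would be extending a stated rule rather than filling a gap.

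**Baseline data are not ignored.** A reader might infer that the Visit 1 scores go unused, or that entry scarring is disregarded throughout objective 1. The documents do not support either reading. Section 10.2 summarises baseline measures by arm. Sections 4.4, 5.1 and 8.1 have a blinded assessor judge scarring progression against the baseline photograph or diagram, so entry scarring is already built into that outcome. The omission is confined to the between-group models for the scored outcomes.

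**No bias.** A reader might also infer that the estimates would be biased. Under randomisation a follow-up comparison without the baseline score is unbiased in expectation. What is lost is precision and protection against chance imbalance. This objection stands in full.

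**The size is assumed.** This also stands. That VASS has a high ρ is plausible from the protocol's description of scarring, but no figure supports it. Section 5.1 also keeps the blinded assessor out of other trial activities, so baseline and follow-up VASS will probably be scored by different people, which could lower ρ. Inclusion criterion 2 requires controlled disease, which narrows the baseline range of global severity and possibly of quality of life.

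**FSFI.** A follow-up-only comparison in a randomised trial is valid, so its schedule is not an error.

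**Conclusion.** The point holds as an improvement to a stated rule. As written, the models for VASS, VQLI, CDLQI and clinician global severity would leave out a baseline value that the trial already collects. For the continuous scores the residual variance could be 9% to 49% lower with it, if ρ after the minimisation factors lies between 0.3 and 0.7. That range is an assumption. The case is strongest for VASS and weakest for global severity, where the gain may be small.

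The primary analysis, the 320/400 sample size, the yes/no scarring outcome, time to first flare and VIN/SCC are unaffected. The missing FSFI baseline is a weaker, separate matter of design preference. It does not make the FSFI comparison invalid.

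**What to change.** **Wording, in section 10.2 and the synopsis.** After "adjusted for the same variables as the primary analysis" add: *and, where measured, the baseline value of the outcome*. No extra data are needed. The cost is a text change in two places, carried into the SAP.

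**Optional.** If recruitment is still open, the sponsor could consider adding FSFI to the adult questionnaires at Visit 1, with a prespecified way to handle adults already randomised without it (for example mean imputation of the baseline, or a missing-baseline indicator). This adds an intimate questionnaire to the first visit and needs an amendment. Section 14.1 allows immediate implementation of minor amendments only for logistical or administrative changes, so the sponsor would have to settle how this one is classified. The benefit depends on how many adults remain to be randomised, which the protocol does not show.

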### 10.3 Planned interim analysis

There is no planned formal interim statistical analysis of treatment effectiveness. However, an integral internal pilot phase will allow a feasibility assessment, examining recruitment, and retention. As part of continuous oversight, the DMC will be provided with confidential reports by trial arm, containing information on recruitment, protocol compliance, safety, and interim assessments of outcomes (between-group estimates of differences in efficacy and/or safety outcomes), as agreed.

### 10.4 Timing for final analyses

Final analyses will be performed once the database has been locked.

### 10.5 Planned subgroup analyses

Subgroup analyses for the primary outcomes will be performed according to age at randomisation (children (<16 years) or adults ( $\geq 16$ )), time since last flare ( $\leq 6$  months,  $> 6$  months), and strength of study TCS (potent or superpotent) by including appropriate interaction terms in the regression models. The trial is not powered to detect any interactions hence the subgroup analyses will be treated as exploratory.

### 10.6 Assessment of safety

Analysis of safety data will be presented descriptively using frequency counts and percentages in each allocated group.

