### 3.3 Secondary objectives

1. Assess the effectiveness of proactive versus reactive use of TCSs over 24 months in reducing disease progression.
2. Assess the clinical effectiveness of proactive versus reactive strategies for the management of vulval LS for up to 24 months.
3. Assess the safety of using potent and superpotent TCSs in the vulval area over 24 months.
4. Assess the cost-effectiveness of the two treatment strategies.
5. Understand the acceptability of reactive and proactive long-term treatment strategies and the barriers and facilitators to continuing with prescribed treatment.

Trial objectives and outcome measures as mapped in Table 2.

Table 2. Mapped objectives and outcome measures

Objective	Outcome Measure	Outcome Time Point	Method
Primary objective			
Compare the effectiveness of proactive versus reactive strategies for using topical corticosteroids on the number of flares within 12 months, in people aged $\geq 5$ years with vulval Lichen Sclerosis	Number of flares	Over 12 months	Text/app/email reminders every two weeks for 12 months Participant reported
Secondary objectives			
1. Assess the effectiveness of proactive versus reactive use of TCS over 24 months in reducing disease progression	Scarring	At 12 and 24 months	Clinical assessment comparing to baseline photographs, if consent given, or comparing to baseline clinical assessment diagram if consent for photographs not obtained.
	VASS	At 12 and 24 months	Clinical assessment
	Development of VIN or vulval SCC	Over 24 months	Clinical assessment/medical notes
2. Assess the clinical effectiveness of proactive versus reactive strategies for the management of vulval Lichen Sclerosis for up to 24 months	Global clinical severity assessment	At 3, 6, 12, 18 and 24 months	Clinical assessment
	Sexual function	At 12 and 24 months	Participant reported
	Time to first flare	At 1 st flare over 12 months	Text/app/email reminders every two weeks for 12 months Participant reported

Objective	Outcome Measure	Outcome Time Point	Method
	Condition specific QoL CDLQI (adolescents and children) and VQLI (adults)	At 3, 6, 12, 18 and 24 months	Questionnaire Participant reported
	Generic utility instrument measured by EQ-5D-5L (adolescents and adults) and CHU-9 (children)	At 3, 6, 12, 18 and 24 months	Questionnaire Participant reported

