### Clinical effectiveness

- Progression of scarring assessed by blinded assessor at 12 and 24 months by comparing post randomisation to baseline photographs (if participant consented), or assessed clinically if consent has not been given for photographs:
  - Adults: scarring worsened (yes/no)
  - Children and adolescents: failure of normal vulval development (clinical assessment) and/or evidence of scarring (yes/no).
- Vulvar Architectural Severity Scale at 12 and 24 months post randomisation (VASS) [30].
- Time to first flare.
- Global clinical severity assessment of LS (5-point ordinal scale) at 3, 6, 12, 18 & 24 months, plus assessed by blinded assessor at 12 and 24 months.
- Condition specific QoL at 3, 6, 12, 18 & 24 months using:
  - Vulvar Quality Life Index (VQLI) (adults) [31]
  - Children's Dermatology Life Quality Index (CDLQI) (adolescents and children) [32].
- Sexual function (adults only) using Female Sexual Function Index [33] at 12 & 24 Months.

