### Safety

- Development of vulval intraepithelial neoplasia or vulval squamous cell carcinoma at 24 months.
- Targeted adverse events e.g. stinging, skin thinning measured by patient reported symptoms and clinical examination from randomisation over 24 months.

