### 10.8 Definition of populations analysed

For the primary analysis, all randomised participants who receive at least one dose of the study medication, will be analysed according to allocated treatment group regardless of adherence to the allocated treatment. This will be supplemented by analysing only the participants who would comply with their allocated intervention. Full definition and cut-off for compliance will be specified in the SAP.

For the secondary outcomes, participants will be analysed according to allocated treatment group regardless of adherence to the allocated treatment.

For the safety outcomes, all randomised participants who receive at least one dose of the study medication will be analysed according to:

- treatment received.

- allocated treatment group regardless of adherence to the allocated treatment.

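### Section 10.6 reports safety only as counts and percentages per allocated group, so the steroid-harm comparison carries no uncertainty, and VIN/SCC falls under two different analysis rules

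*Protocol*

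**What the plan says.** - Protocol 10.6 fixes the safety method: "Analysis of safety data will be presented descriptively using frequency counts and percentages in each allocated group". It mentions no between-arm estimate or interval.
- Protocol 3.3 makes safety the third secondary objective: "Assess the safety of using potent and superpotent TCSs in the vulval area over 24 months". The synopsis lists Safety under its secondary outcomes, and section 4.4, which is the secondary-endpoint section, contains a Safety list.
- Protocol 10.2 covers secondary outcomes: "Between-group comparison of secondary outcomes will be based on an appropriate regression model for the outcome". A non-parametric estimator is allowed instead, and the adjustment variables are those of the primary analysis, that is, the minimisation factors.
- Protocol 10.8 gives two population rules. One reads "For the secondary outcomes, participants will be analysed according to allocated treatment group regardless of adherence to the allocated treatment". The other begins "For the safety outcomes, all randomised participants who receive at least one dose of the study medication will be analysed according to" and then names two groupings, treatment received and allocated group.
- VIN/SCC appears twice. Table 2 in section 3.3 maps "Development of VIN or vulval SCC" to the first secondary objective, on disease progression. The Safety list in 4.4 has "Development of vulval intraepithelial neoplasia or vulval squamous cell carcinoma at 24 months". Section 11.4 also has pre-cancerous change among its targeted adverse events.

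**The concern.** The trial has to weigh fewer flares against local harm from steroid applied twice a week for two years. Section 2.6 of the protocol itself notes how little evidence there is to quantify that harm. A report that follows 10.6 to the letter would give one percentage per arm and leave the reader to judge the difference by eye. Two percentages that look far apart may be compatible with no difference, and two that look alike may be compatible with a material one.

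For VIN/SCC there is a second problem. Under 10.2 the planned result is a between-group comparison; under 10.6 it is a line in a count table. No sentence says which applies to an outcome that sits in both classes, so the choice for a cancer-related outcome stays open until someone makes it.

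**Working it through.** **Plan's own figure.** There is none to reproduce here: the protocol gives no safety event rates and no precision target for safety. The counts below are assumptions.

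**1. Which rule applies to which outcome**

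| Outcome | Where listed | Rule in 10.2 | Rule in 10.6 |
|---|---|---|---|
| Local atrophic events (thinning, striae, telangiectasia) | Safety in 4.4 (targeted events; skin thinning is an example); detailed in 11.4 | Reached only because 4.4 is the secondary-endpoint section | Yes |
| VIN/SCC | Objective 1 in Table 2; Safety in 4.4 | Yes | Yes |
| Progression of scarring | Clinical effectiveness in 4.4, blinded; targeted event in 11.4 | Yes | No: 11.4 governs event reporting, not analysis |

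So 10.6 works as the specific rule for safety, but no exception to 10.2 is stated. VIN/SCC is the one outcome for which both rules clearly apply.

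**2. What an interval would show**

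Inputs: 400 randomised 1:1 (10.1), so 200 per arm. Loss to follow-up is put at 5-10% in 10.1; taking 10%, 200 x 0.90 = 180 per arm.

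Method: Newcombe interval from the Wilson limits (l, u) of each arm, with d = p1 - p2:
- lower = d - sqrt[(p1 - l1)^2 + (u2 - p2)^2]
- upper = d + sqrt[(u1 - p1)^2 + (p2 - l2)^2]

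Worked case, 18 versus 9: p1 = 10.0% (Wilson 6.42 to 15.25) and p2 = 5.0% (Wilson 2.65 to 9.23).
- d = 5.0
- lower = 5.0 - sqrt(3.58^2 + 4.23^2) = 5.0 - 5.54 = -0.54
- upper = 5.0 + sqrt(5.25^2 + 2.35^2) = 5.0 + 5.75 = 10.75

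| Assumed events per 180 | Difference (points) | 95% interval |
|---|---|---|
| 0 v 0 | 0 | -2.1 to 2.1 |
| 2 v 2 (1%) | 0 | -3.0 to 3.0 |
| 5 v 5 (3%) | 0 | -3.9 to 3.9 |
| 9 v 9 (5%) | 0 | -4.8 to 4.8 |
| 18 v 18 (10%) | 0 | -6.4 to 6.4 |
| 2 v 0 | 1.1 | -1.1 to 4.0 |
| 9 v 5 | 2.2 | -2.0 to 6.7 |
| 18 v 9 | 5.0 | -0.5 to 10.8 |

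**3. Can the 10.2 regression serve VIN/SCC?**

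The minimisation factors in section 5 are site, four age bands, time since last flare (two levels) and potency (two levels). Before any site term the model has 1 intercept + 1 treatment + 3 age + 1 time + 1 potency = 7 coefficients. If only 0 to 2 cases occur (assumed), it cannot be fitted reliably. An unadjusted difference can still be given, as the 0 v 0 and 2 v 0 rows show.

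**4. Does the difference between the two 10.8 populations matter?**

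A reactive participant with no flare takes no dose. At the design rate of 4 a year with dispersion 0.34 (10.1), the probability of no flare in 24 months is:
- with persistent individual rates, (1 + 0.34 x 8)^(-1/0.34) = 0.021, or 4.2 of 200;
- with independent years, [(1 + 0.34 x 4)^(-1/0.34)]^2 = 0.080^2 = 0.0064, or 1.3 of 200.

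About 1 to 4 participants is negligible. The issue is the method, not the population.

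**The case against.** The strongest reply is that descriptive safety reporting is ordinary practice. Objective 3, unlike objectives 1 and 2, is not worded as a comparison of arms. Section 10.2 promises a full SAP, which could add intervals, and section 10.3 already foresees between-group safety estimates for the data monitoring committee. Rare events would give a test almost no power. All of this stands, and it is why the point is minor. It does not remove the point: 10.6 names a method without deferring it, whereas 10.8 expressly leaves the compliance definition to the SAP. What is proposed is an interval, not a test.

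Four stronger readings are tempting, and the document does not support them.
- A reader might infer that 10.6 and 10.8 contradict each other on grouping. They do not. 10.6 does not say it is the only grouping, and both can be followed together; a cross-reference is enough.
- A reader might infer that scarring also has two competing rules. It is a blinded effectiveness outcome ("Progression of scarring assessed by blinded assessor at 12 and 24 months"), so 10.2 applies. Its entry in 11.4 tells sites what to report and sets no analysis.
- A reader might want a difference for any targeted adverse event. That list includes scarring and local burning, pain and pruritus. The synopsis footnote counts itching, burning and pain as symptoms of the disease. Such a composite would mix disease activity, which proactive therapy may reduce, with steroid harm, and could hide the harm.
- A reader might conclude that section 1.5 is wrong to say the proactive group is at no higher risk. The same section acknowledges local risk from long-term use, and the point is peripheral to the analysis of safety.

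**Conclusion.** The point holds as a cheap improvement of minor severity. Section 10.6 leaves the steroid-harm comparison without any statement of uncertainty, and VIN/SCC is subject to two rules with nothing to say which governs. At assumed event rates of 1% to 10% and 180 per arm, the missing information is an interval of about 3 to 6 points either side of the observed difference, enough to change how a 10% versus 5% result is read. These sizes rest on assumed event counts and on 10% loss; the protocol supplies no rates. The primary analysis and the sample size are untouched.

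**What to change.** In 10.6, for local atrophic events (thinning, striae, telangiectasia) and for VIN/SCC:
- report the number and percentage per arm plus the unadjusted risk difference with a 95% confidence interval (Newcombe, for example) and no test, by allocated group;
- give treatment received as the second presentation, with a reference to 10.8;
- state that this replaces the 10.2 regression for these endpoints.

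Keep blinded scarring progression under 10.2, and do not form a composite of all targeted adverse events.

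Cost: two or three sentences and one extra table column, with no new data and no change to endpoints. The downside is that the intervals will be wide and will often exclude neither no difference nor a material one; the report should say so.
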